14.1. Overview of the Study Design

This is a single-arm, open label, phase Ib study of Ibrutinib in combination with lenalidomide and dexamethasone in adult (age 18 years and older) patients with relapsed/refractory MM. A 3+3 phase I clinical trial design as described in Section 6.0 was chosen to determine the MTD of Ibrutinib in combination with lenalidomide given on days 1-21 of a 28-day cycle and dexamethasone given orally weekly. An expansion cohort of 10 patients will be treated at the MTD to gather additional safety and anti-tumor activity data.

As of April 15, 2021, 2 patients have been enrolled onto dose level 2.

- If none of the first 3 patients treated at dose level 2 develops a DLT, then the next cohort of 3 patients will be enrolled onto dose level 3 and biospecimen collection will begin for all subsequent patients enrolled.
- If one of the 3 patients treated at dose level 2 develops a DLT, then the next cohort of 3 patients will be enrolled at dose level 2 and correlative biospecimens will be collected from these patients.
 - o If 2 or more of the 6 patients treated at dose level 2 develops a DLT then an additional 10 patients will be enrolled onto dose level 1 so that a total of 10 patients will have provided biospecimens at the MTD. (Note: Total sample size will be 6 [from dose level 1] + 6 [from dose level 2] + 10 [for dose expansion] = 22. Biospecimens will be available for 10 patients treated at the MTD.)
- If 2 or more of 3 patients treated at dose level 2 has an DLT, an additional 10 patients will be enrolled onto dose level 1 to further assess safety and collect specimens for correlative aims. (Note: Total sample size will be 6 [from dose level 1] + 3 [from dose level 2] + 10 [for dose expansion] = 19. Biospecimens will be available for 10 patients treated at the MTD.)
- If at most 1 of 6 patients treated at dose level 2 develops a DLT and 2 or more of the 3-6 patients treated at dose level 3 develops a DLT, then an additional 7 patients will be enrolled onto dose level 2 so that a total of 10 patients will have provided biospecimens at the MTD. (Note: Total sample size will be 6 [from dose level 1] + 6 [from dose level 2] + 6 [maximum number anticipated on dose level 3] + 7 [for dose expansion] = 25. Biospecimens will be available for 10 patients treated at the MTD.)
- If at most 1 of 6 patients treated at dose level 2 develops a DLT and 1 or fewer of the 6 patients treated at dose level 3 develops a DLT, then an additional 4 patients will be onto dose level 3 so that a total of 10 patients will have provided biospecimens at the MTD. (Note: Total sample size will be 6 [from dose level 1] + 6 [from dose level 2] + 6 [maximum number anticipated on dose level 3 to establish it as MTD] + 4 [for dose expansion] = 22. Biospecimens will be available for 10 patients treated at the MTD.)
- If at most 1 of 6 patients treated at dose level 3 develops a DLT then an additional 4 patients will be enrolled onto dose level 3 so that a total of 10 patients will have provided biospecimens at the MTD. (Note: Total sample size will be 6 [from dose level 1] + 3

[from dose level 2] + 6 [maximum number anticipated on dose level 3] + 4 [for dose expansion] = 19. Biospecimens will be available for 10 patients treated at the MTD.)

- If 2 or more of the 3-6 patients treated at dose level 3 develops a DLT then an additional 7 patients will be enrolled onto dose level 2 so that a total of 10 patients will have provided biospecimens at the MTD. (Note: Total sample size will be 6 [from dose level 1] + 3 [from dose level 2] + 6 [maximum number anticipated on dose level 3] + 7 [for dose expansion] = 22. Biospecimens will be available for 10 patients treated at the MTD.)

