Secondary Objectives	
To determine the following:
 
 1. Progression-free survival (PFS): Time from registration to disease progression or death due to any cause. 2. Overall survival (OS): Time from registration to death due to any cause. 3. Overall Response Rate: Time from start of treatment to objective response 4. Duration of response: Time from documented response to disease progression among those patients whose disease meets the IMWG criteria for disease response
Correlative Science Objectives	To perform select immunologic studies with this combination therapy.
Study Design	
Part 1: Dose Escalation
 
Patients in the dose escalation phase will receive oral treatment with:
 
Ibrutinib: Days 1-28 of every 28-day cycle Lenalidomide: Days 1-21 of every 28-day cycle Dexamethasone: 40 mg for patients <75 at the time of registration 20 mg for patients ≥ 75 at registration on Days 1, 8, 15 and 22 of every Cycle. One cycle is 28 days.
 
Starting doses of ibrutinib and lenalidomide will be assigned at the time of registration. A minimum of 2 or a maximum of 6 patients will be accrued to a given dose level. Doses will not be escalated in any individual patient. If none of the first 3 patients treated at a given dose level develops a DLT during the first cycle of treatment, enrollment to the dose level will be closed and enrollment will reopen at next higher dose level. If there are no other higher dose levels to be tested, three additional patients will be enrolled at the current dose level to confirm MTD. If one of the first 3 patients treated at a given dose level develops a DLT during the first cycle of treatment, three additional patients will be enrolled onto the current dose level. If, at any time in the enrollment of these 3 additional patients, a patient develops a DLT, enrollment will be closed to this dose level. Enrollment will be reopened to the next lower dose level if fewer than 6 patients have been treated at that dose level. If none of these 3 additional patients develops a DLT during the first cycle of treatment, enrollment to this dose level will be closed and enrollment will reopen at next higher dose level. If

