1.2. Study Design

This is a single-arm, open label, phase Ib study of Ibrutinib in combination with lenalidomide and dexamethasone in adult (age 18 years and older) patients with relapsed/refractory MM. A dose-escalation will be completed with the primary endpoint of determining safety, tolerability and maximum tolerated dose (MTDs) in a standard 3+3 design over 3 dose levels of 560, 560 and 840 mg of Ibrutinib given orally daily, lenalidomide given at 15 mg, 25 mg and 25 mg orally daily on days 1-21 of a 28-day cycle and dexamethasone 40 mg given orally weekly (patients 75 yrs and older will start with Dexamethasone20 mg) (Table 3 and 4). Patients with GFR 30-60 ml/min will receive lenalidomide 10 mg daily, days 1 – 21 of 28 according to manufacturer's recommendation. A minimum of 6 and a maximum of 18 patients will be recruited in the phase I portion. Upon identification of the MTD for the dose level combination of Ibrutinib and lenalidomide/dexamethasone, a 10-patient expansion cohort will commence. Secondary endpoints of progression-free survival, overall survival, duration of response, and pharmacokinetic and pharmacodynamics of Ibrutinib in combination with lenalidomide and dexamethasone will be assessed.

Please see Section 7 for dexamethasone dose modification guidelines.

Version Date 22-Jan-2024

CONFIDENTIAL

Version # 3.0

Table 3 Dose Level

	Ibrutinib	Lenalidomide	Dexamethasone^a
1 (starting dose)	560 mg	15 mg	40mg
2	560mg	25 mg	40mg
3	840mg	25 mg	40mg

^a The starting dose of dexamethasone will be reduced to 20 mg based on tolerability or if the patient is 75 years or older at the time of registration.

Table 4 Dosing Schedule

Agent	Dose	Route	Days	ReRx
Ibrutinib	assigned at time of registration	Oral	1-28	
Lenalidomide	assigned at time of registration	Oral	1-21	
Dexamethasone	40 mg if age < 75 years old at registration	Oral	1,8,15, 22	Every 28 days
	20 mg if age ≥ 75 years old at registration			

Please see section 7.1 for the definition of Dose Limiting Toxicity (DLT) occurring during combination of lenalidomide, dexamethasone and Ibrutinib.

Determination of Maximum Tolerated Dose (MTD)

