The maximum tolerated dose is defined as the highest dose level among those tested where at most 1 out of 6 patients develops a DLT prior to the start of their second cycle of treatment and the next highest dose level is such that 2 or more out of a maximum of 6 patients treated at this dose level developed a DLT prior to the start of their second cycle of treatment.

Enrollment and determination of MTD

A minimum of 2 or a maximum of 6 patients will be accrued to a given dose level. Doses will not be escalated in any individual patient. If none of the first 3 patients treated at a given dose level develops a DLT during the first cycle of treatment, enrollment to the dose level will be closed and enrollment will reopen at next higher dose level. If there are no other higher dose levels to be tested, three additional patients will be enrolled at the current dose level to confirm MTD. If one of the first 3 patients treated at a given dose level develops a DLT during the first cycle of treatment, three additional patients will enroll onto the current dose level. If, at any time in the enrollment of these 3 additional patients, a patient develops a DLT, enrollment will be closed to this dose level. Enrollment will be re-opened to the next lower dose level if fewer than

6 patients have been treated at that dose level. If none of these 3 additional patients develops a DLT during the first cycle of treatment, enrollment to this dose level will be closed and enrollment will reopen at next higher dose level. If there are no other higher dose levels to be tested, this will be considered the MTD.

For this protocol, the patient must return to their registration institution for evaluation and continuation of treatment (at least every 28 ± 3 days) according to the test schedule. Patients who have not had disease progression and have experienced acceptable toxicity will be eligible to continue protocol retreatment at their current dose level until disease progression, unacceptable toxicity, or refusal. Those patients who have not progressed and who have experienced unacceptable toxicity may be eligible to continue protocol retreatment at a lower dose.

Criteria for discontinuation of all protocol therapy include:

- Tumor progression
- Request by the patient to withdraw
- Unacceptable adverse events
- Treatment delay of >4weeks

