- Intercurrent illness which would, in the judgment of the investigator, affect assessments of clinical status to a significant degree or require discontinuation of drug
- Non-protocol chemotherapy, or an experimental drug during the trial

Patients who discontinue treatment for any of the above reasons will go to survival follow-up. Once a patient has entered the survival follow-up phase of the trial, his/her therapy is at the discretion of the treating physician. The sponsor would like to collect that information, if the patient agrees.

Patients who discontinue treatment due to toxicity should be monitored until resolution or stabilization of adverse event.

Expansion cohort

Once the MTD has been established or determined, 10 additional patients will be treated at the MTD. The total number of patients to be enrolled in the study will be 28.

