2.4.2 Correlative

1. Immunologic studies: bone marrow aspirate and peripheral blood samples will be collected from patients for immunome studies. See Protocol Section 13 for more information.

3. Patient Selection / Population

19-25 patients (9-18 dose escalation; 4-10 dose expansion) with symptomatic multiple myeloma (as defined by IMWG criteria) will be enrolled across multiple investigational sites in the United States. Screening labs must be performed within 7 days prior to registration. Complete body CT scan if clinically indicated at screening must be performed within 14 days prior to registration.

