7.3. Enrollment and determination of MTD

A minimum of 2 or a maximum of 6 patients will be accrued to a given dose level. Enrollment will begin with 3 patients accrued to dose level 1.

Dose de/escalation scheme for Dose 1:

- If none of the first 3 patients treated at dose level 1 develops a DLT during the first cycle of treatment, then the next cohort of 3 patients will be enrolled at dose level 2.
- If one of the first 3 patients treated at dose level 1 develops a DLT during the first cycle of treatment, then an additional cohort of 3 patients will be enrolled at the current dose level.
- If at most 1 of the 6 patients enrolled at dose level 1 develops a DLT during the first cycle of treatment, the next cohort of 3 patients will be treated at dose level 2.
- If 2 or more of the 6 patients enrolled at level 1 develops a DLT during the first cycle of treatment, enrollment will be halted, and the study team will discuss whether to

submit an amendment to reopen enrollment to a lower dose level.-

As of October 7, 2021, 3 patients have been enrolled onto dose level 2.

Dose de/escalation scheme for Dose 2:

- If none of the first 3 patients treated at dose level 2 develops a DLT during the first cycle of treatment, then the next cohort of 3 patients will be enrolled onto dose level 3.
- If one of the 3 patients treated at dose level 2 develops a DLT during the first cycle of treatment, then the next cohort of 3 patients will be enrolled at dose level 2.
 - If 2 or more of the 6 patients treated at dose level 2 develops a DLT then an additional 10 patients will be enrolled onto dose level 1 before completing enrollment.
- If 2 or more of 3 patients treated at dose level 2 develops a DLT during the first cycle of treatment, an additional 10 patients will be enrolled onto dose level 1 to further assess safety before completing enrollment.

Dose de/escalation scheme for Dose 3 (if applicable):

- If at most 1 of 6 patients treated at dose level 2 develops a DLT during the first cycle of treatment and 1 or fewer of the 6 patients treated at dose level 3 develops a DLT in the first cycle of treatment, then an additional 4 patients will be treated on dose level 3 before completing enrollment.

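### The fixed expansion of 10, total of 28, minimum of 6 and 42–48 months fit an 18 + 10 design, not the enrolment paths in 7.3 and 14.1; one specimen count and the ORR population also need correcting

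*Combined protocol and SAP*

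**What the plan says.** **Fixed figures.** Section 1.2 states "A minimum of 6 and a maximum of 18 patients will be recruited in the phase I portion", then that "a 10-patient expansion cohort will commence" once the MTD is identified, and under its expansion heading "The total number of patients to be enrolled in the study will be 28". Section 14.1 repeats the fixed size: "An expansion cohort of 10 patients will be treated at the MTD to gather additional safety and anti-tumor activity data". Section 14.2 gives 6 to 25 patients in total and, from its accrual rates, about 42 to 48 months.

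**Path-based figures.** Section 3 gives "19-25 patients (9-18 dose escalation; 4-10 dose expansion", and the synopsis agrees. Sections 7.3 and 14.1 add 10 patients at level 1, 7 at level 2 or 4 at level 3, depending on where the MTD falls. Section 7.3 also reports "As of October 7, 2021, 3 patients have been enrolled onto dose level 2".

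**Return to a lower level.** The synopsis says "Enrollment will be reopened to the next lower dose level if fewer than 6 patients have been treated at that dose level", and Section 1.2 repeats this. For the case where level 3 proves too toxic, 7.3 adds 7 patients at level 2 and then completes enrolment.

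**Specimens.** Under 14.1, if the first 3 patients at level 2 have no DLT, level 3 opens and collection starts with later patients only. Every path there that ends in an expansion claims specimens from 10 patients at the MTD.

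**Response rate.** Section 14.3.2 makes it the primary endpoint of the expansion portion, counts patients who began treatment, and puts a 90% binomial interval on the overall rate. Sections 2.2 and 2.4.1 list it as secondary, and the synopsis describes it as a time. Patient Evaluability takes all eligible treated patients. The secondary-endpoint statement ties PFS and OS to the expansion cohort and tabulates response by dose level.

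**The concern.** The current text gives sites, IRBs and the DSMB several different trial sizes. Section 14.1 contradicts itself, because its fixed expansion of 10 is followed by paths that add 7 or 4. A duration presented as following from stated rates should follow from them.

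Two consequences go beyond editing. The correlative work is planned around 10 patients: 13.2 wants at least 40 longitudinal samples, which is 10 patients at 4 time points. And if the response denominator is left open in an open-label trial, it can be settled after responses are known.

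**Working it through.** **Inputs.** Path sizes come from 7.3 and 14.1: 6 patients at level 1 as 14.1 counts them, and 3–6 at level 3 where it proves too toxic. Rates come from 14.2: a cohort of 3 every 4–6 months, a 2-month gap, then 1 expansion patient per month.

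**Formulas.** Total = level 1 + level 2 + level 3 + expansion. Months = (escalation patients ÷ 3) × (4 to 6) + 2 + expansion patients.

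**The plan's own figures.** 28 is the escalation maximum of 18 plus a fixed expansion of 10. For that design, 6 cohorts give 6 × 5 + 2 + 10 = 42 and 6 × 6 + 2 + 10 = 48 months. This reproduces 42–48 only at 5–6 months per cohort; at 4 months it is 6 × 4 + 2 + 10 = 36.

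**Current paths, in the order of 14.1:**

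| DLT outcome | Patients | Total (14.1 states) | Months | At MTD level | MTD patients with specimens |
|---|---|---|---|---|---|
| Level 2 fails after 6 | 6+6+10 | 22 (22) | 28–36 | 6+10 = 16 | 10 |
| Level 2 fails after 3 | 6+3+10 | 19 (19) | 24–30 | 6+10 = 16 | 10 |
| Level 2 passes with 6, level 3 fails | 6+6+(3–6)+7 | 22–25 (25) | 29–45 | 6+7 = 13 | 3+7 = 10 |
| Level 2 passes with 6, level 3 passes | 6+6+6+4 | 22 (22) | 30–42 | 6+4 = 10 | 6+4 = 10 |
| Level 2 has 0/3, level 3 passes | 6+3+6+4 | 19 (19) | 26–36 | 6+4 = 10 | 6+4 = 10 |
| Level 2 has 0/3, level 3 fails | 6+3+(3–6)+7 | 19–22 (22) | 25–39 | 3+7 = 10 | 0+7 = 7 |

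The six sums in 14.1 are correct. Overall, escalation is 9–18, the total 19–25 and the duration 24–45 months. No path reaches 28 patients or 48 months.

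**Minimum of 6.** With 6 patients at level 1 and 3 already at level 2, at least 9 were enrolled.

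**Specimens on the last path.** The first 3 level 2 patients precede collection, so only the 7 added later contribute. Section 13.2 also confines the immunome assay to the expansion phase, at 4 time points: 10 patients give 40 samples, 7 give 28 and 4 give 16. The 40 planned are therefore met from expansion patients only when level 1 is the MTD.

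**Level 2 on the last path.** The MTD definition allows at most 1 DLT in 6 patients. Only 3 have been treated at level 2 when 7.3 opens the 7-patient expansion. The synopsis and 1.2 would reopen level 2 under the 3+3 rule, to at most 6 patients. Section 7.3 passes 6 with no check and no stated action if DLTs occur.

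**Effect of the response denominator.** No target rate is stated, so about 50% is assumed for illustration. Exact (Clopper-Pearson) 90% intervals:

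- Expansion only: 2/4, 10–90%; 4/7, 23–87%; 5/10, 22–78%.
- All treated at the MTD level: 5/10, 22–78%; 7/13, 29–78%; 8/16, 28–72%.
- All treated, any level: 11/22, 31–69%; 12/25, 30–66%.

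**The case against.** The best defence is that the operative text is sound. The paths add up, the synopsis and Section 3 give the right ranges, the maximum of 25 in 14.2 agrees, and no dose decision or test depends on 28, 6 or 48. The minimum of 6 had a source, since 2 or more DLTs among 6 patients at level 1 would have halted enrolment. The 42–48 months is labelled approximate and overlaps the longest path. All of this stands. It makes the figures outdated rather than badly calculated, but they remain in the current text as statements of fact.

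Four stronger readings are tempting and are not supported:

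- A reader might infer that 28 patients and 48 months come from an unlisted path in which level 2 is reopened, fails, and 10 patients go to level 1. The figures in 1.2 already give 18 + 10 = 28, and the 14.2 rates then give 42–48.
- A reader might infer that the synopsis and 7.3 give opposite instructions after level 3 fails. Both return to level 2. The gap is how many patients are added and what follows if they have DLTs.
- A reader might infer that no response denominator exists, or that the primary rate must rest on 4 patients. Section 14.3.2 does name a denominator, patients who began treatment. The ambiguity is that the endpoint is assigned to the expansion portion while the rate is called overall.
- A reader might infer that pooling everyone assigned to the MTD is the only correct set. It is one acceptable choice, and counting assigned rather than treated patients would depart from 14.3.2 and Patient Evaluability.

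A restated 24–45 months would also rest on planning rates that may be optimistic. Level 2 had 2 patients on 15 April 2021 (14.1) and 3 on 7 October 2021 (7.3).

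**Conclusion.** The point holds. Against the current paths, the fixed expansion of 10 should read 10, 7 or 4; the total of 28 and the minimum of 6 should read 19–25; the escalation minimum of 6 should read 9; and 42–48 months should read about 24–45 at the stated rates. The last path yields specimens from 7 MTD patients, not 10, and leaves DLTs among the added level 2 patients without a rule. The response rate has two statuses and a population that can be read as 4–10, 10–16 or 19–25 patients.

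This rests on 14.1's count of 6 at level 1 and on 3–6 patients at level 3. The general minimum of 2 per level would allow 6 + 3 + 2 + 7 = 18, but 7.3 and 14.1 both say 3–6 at level 3. That the outdated figures are a carry-over from an 18 + 10 design is an inference from the arithmetic; the documents do not say so. The intervals are illustrative.

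**What to change.** 1. In 1.2, 14.1 and 14.2, state the expansion as 10, 7 or 4 by MTD level, escalation as 9–18 and the total as 19–25. Delete 28 and both minimum-of-6 statements.
2. Restate accrual as about 24–45 months at the stated rates, or update the rates to observed accrual and recompute.
3. Correct the last-path specimen count to 7. If 10 are needed, add 10 patients instead of 7 there: 6 + 3 + (3–6) + 10 = 22–25, within the maximum. Note beside the specimen counts that 13.2 limits the immunome assay to the expansion phase.
4. Make the synopsis and 1.2 defer to 7.3. On the last path, apply the MTD rule (at most 1 of 6 with a DLT) to the first 3 patients added at level 2, and state what happens if it fails. If the answer is a 10-patient expansion at level 1, list that path, because it can reach 6 + 6 + 6 + 10 = 28 patients and 48 months.
5. Define the response rate as a proportion with one status throughout, and name one treated-patient denominator for the 90% interval before responses are reviewed. Treated patients assigned to the MTD level (10, 13 or 16), with expansion-only and all-treated results alongside, is a reasonable choice. State the PFS and OS population in the same place.

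The cost is wording, with no added patients unless the sponsor takes the option in item 3 (3 more) or a level 1 expansion in item 4. The check in item 4 turns 3 of the 7 added patients into one more cohort, so that path takes 5 × 4 + 2 + 4 = 26 to 6 × 6 + 2 + 4 = 42 months, still inside 24–45.

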2.4. Endpoints

2.4.1 Primary and Secondary

Primary:

1. Maximum tolerated dose (MTD): The maximum tolerated dose (MTD) is defined as the highest dose level among those under consideration where at most 1 of 6 patients develops a dose limiting toxicity and 2 or more of the 3-6 patients treated at the next higher dose level develop a dose limiting toxicity.
2. Safety profile: The maximum grade of each type of toxicity will be recorded for each patient. For each toxicity reported by dose level, the percentage of patients developing any degree of that toxicity as well as the percentage of patients developing a severe degree (Grade 3 or higher) due to treatment will be determined.

Secondary:

1. Progression free survival (PFS) defined as the time from study entry to the documentation of disease progression using IMWG criteria or death due to any cause.
2. Overall survival (OS) is defined as time from registration to death due to any cause.
3. Overall Response rate(ORR)
4. Duration of response, defined as the time from documented response to disease progression among those patients whose disease meets the IMWG criteria for disease response.
5. Safety Profile: CTCAE v5.0 will be used to grade and assign attribution to each adverse event reported.

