7.2. Determination of Maximum Tolerated Dose (MTD)

The maximum tolerated dose is defined as the highest dose level among those tested where at most one out of 6 patients develops a DLT prior to the start of their second cycle of treatment and the next highest dose level is such that 2 out of a maximum of 6 patients treated at this dose level developed a DLT prior to the start of their second cycle of treatment.

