- If at most 1 of 6 patients treated at dose level 2 develops a DLT during the first cycle of treatment and 2 or more of the 3-6 patients treated at dose level 3 develops a DLT during the first cycle of treatment, then an additional 7 patients will be enrolled onto dose level 2 before completing enrollment.
- If at most 1 of 6 patients treated at dose level 3 develops a DLT during the first cycle of treatment then an additional 4 patients will be enrolled onto dose level 3 before completing enrollment.
- If 2 or more of the 3-6 patients treated at dose level 3 develops a DLT during the first cycle of treatment then an additional 7 patients will be enrolled onto dose level 2 before completing enrollment.

8. Dose and Treatment Modifications

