14.3.2 Statement for Primary Endpoint

The primary endpoint of the dose escalation portion of this phase I study is the MTD. The maximum tolerated dose is defined as the highest dose level among those tested where at most one out of 6 patients develops a DLT prior to the start of their second cycle of treatment and the next highest dose level is such that 2 or more patients among the maximum of 6 patients treated at that dose level developed a DLT prior to the start of their second cycle of treatment.

The primary endpoint of the expansion portion of this phase I study is the objective response rate. The objective response rate is the percent of patients who meet the International Myeloma Working Group Response Criteria for sCR, CR, VGPR, or PR on two consecutive evaluations at least 4 weeks apart among the patients who began study treatment. A 90% binomial confidence interval will be constructed for the overall objective response rate.

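### If dose level 2 clears at 0/3 and dose level 3 then fails, Section 14.1 names dose level 2 the MTD without the 6-patient check, and counts 10 specimen donors there when its own rule gives 7

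*Combined protocol and SAP*

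**What the plan says.** Four sections (1.2, 2.4.1, 7.2 and 14.3.2) define the MTD by the same standard. In 14.3.2 it is the highest level tested "where at most one out of 6 patients develops a DLT prior to the start of their second cycle"; 2.4.1 has "highest dose level among those under consideration where at most 1 of 6 patients develops a dose limiting toxicity" and 7.2 has "highest dose level among those tested where at most one out of 6 patients develops a DLT".

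The last branch of 14.1 covers failure at dose level 3: "If 2 or more of the 3-6 patients treated at dose level 3 develops a DLT then an additional 7 patients will be enrolled" at dose level 2. After 6 patients at dose level 1, its note adds "3 [from dose level 2] + 6 [maximum number anticipated on dose level 3] + 7 [for dose expansion] = 22". The bullet does not state how dose level 2 had performed, but under 7.3 dose level 3 opens with only 3 patients at dose level 2 if none of those 3 had a DLT. The branch is therefore 0/3 at dose level 2 followed by failure at dose level 3.

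The same note says "6 [maximum number anticipated on dose level 3] + 7 [for dose expansion] = 22. Biospecimens will be available for 10 patients", meaning donors treated at the MTD. When specimens start is set earlier in 14.1: after 0/3 at dose level 2, the "next cohort of 3 patients will be enrolled onto dose level 3 and biospecimen collection will begin for all subsequent patients enrolled".

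Section 7.3 has the matching rule, "then an additional 7 patients will be enrolled onto dose level 2 before completing enrollment". It does not name an MTD or call the 7 patients expansion, but it gives no DLT decision on them either.

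**The concern.** The MTD is the primary endpoint of the escalation part. In this branch 14.1 attaches the label to dose level 2 when 3 patients there have been assessed for DLT, while the definition asks for 6. Seven more patients are then treated at that dose, so the data for a 6-patient check will exist. What is missing is the rule to use them and the action if 2 or more of 6 have a DLT. A team following 14.1 could report as MTD a level that has not met the plan's own definition.

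The synopsis and 1.2 contain a rule that reopens the next lower level when it has fewer than 6 patients. As worded, it follows a DLT among the 3 additional patients at the higher level, so it conflicts with this branch only when dose level 3 fails that way. When dose level 3 fails in its first 3, the conflict is with the MTD definition alone.

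The donor count is a separate and smaller matter. It is a correction to a note on the correlative studies and does not affect dose selection.

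**Working it through.** **1. The plan's own figures.** Totals by branch of 14.1 (dose level 1 + 2 + 3 + expansion), and donors at the MTD (escalation patients at that level enrolled after collection began + expansion patients):

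| Branch | Total | Stated | Donors at MTD | Stated |
|---|---|---|---|---|
| Level 2 fails at 6, expand level 1 | 6+6+0+10 = 22 | 22 | 0+10 = 10 | 10 |
| Level 2 fails at 3, expand level 1 | 6+3+0+10 = 19 | 19 | 0+10 = 10 | 10 |
| Level 2 passes at 6, level 3 fails | 6+6+6+7 = 25 | 25 | 3+7 = 10 | 10 |
| Level 2 passes at 6, level 3 passes | 6+6+6+4 = 22 | 22 | 6+4 = 10 | 10 |
| Level 2 at 0/3, level 3 passes | 6+3+6+4 = 19 | 19 | 6+4 = 10 | 10 |
| Level 2 at 0/3, level 3 fails | 6+3+6+7 = 22 | 22 | 0+7 = **7** | 10 |

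All six totals reproduce. The donor count reproduces in five branches and fails in the last. Ten is the number treated at dose level 2 in that branch (3+7), but the first 3 were enrolled before collection began. The 3 to 6 dose-level-3 patients also donate, giving 10 to 13 donors in all, but not at the MTD.

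**2. Size of the missing check.** The documents give no DLT rates, so the true rates p2 and p3 at levels 2 and 3 are assumed. Everything is conditional on dose level 2 being opened. Write b(k) for the binomial probability of k DLTs in 3 patients.

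- A level passes at 6 patients with probability S(p) = b(0)[b(0) + b(1)] + b(1)b(0). This applies at dose level 3 because the synopsis and 1.2 add 3 patients at the top level after 0/3.
- Dose level 3 fails with probability F = 1 − S(p3).
- The branch is entered with probability (1 − p2)³ × F.
- The next 3 patients at dose level 2 would show 2 or more DLTs with probability q = b(2) + b(3) at p2.
- The branch names dose level 2 although its first 6 patients would fail the definition with probability (1 − p2)³ × F × q.

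| p2 / p3 | (1 − p2)³ | F | Branch entered | q | Named but fails at 6 |
|---|---|---|---|---|---|
| 10% / 30% | 0.729 | 0.580 | 0.423 | 0.028 | 0.0118 |
| 20% / 40% | 0.512 | 0.767 | 0.393 | 0.104 | 0.0408 |
| 30% / 50% | 0.343 | 0.891 | 0.305 | 0.216 | 0.0660 |
| 40% / 60% | 0.216 | 0.959 | 0.207 | 0.352 | 0.0729 |
| 50% / 70% | 0.125 | 0.989 | 0.124 | 0.500 | 0.0618 |

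A simulation of 400,000 trials per pair gave 0.0115, 0.0402, 0.0658, 0.0726 and 0.0623.

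**3. Overall chance that dose level 2 is named the MTD.** As written: [b(0) + b(1)b(0)] at p2, times F. With 6 patients required: S(p2) × F. In row order the pairs are 52.5% vs 51.4%, 54.3% vs 50.2%, 44.0% vs 37.4%, 29.7% vs 22.4% and 17.0% vs 10.8%. The differences match the last column above, up to rounding.

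**4. How often the reopening rule conflicts as well.** Among entries to the branch, dose level 3 fails in its first 3 with probability [b(2) + b(3) at p3]/F:

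- 0.216/0.580 = 37.3%
- 0.352/0.767 = 45.9%
- 0.500/0.891 = 56.1%
- 0.648/0.959 = 67.6%
- 0.784/0.989 = 79.3%

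The reopening rule therefore conflicts in at most 62.7% of entries at 10%/30%, falling to 20.7% at 50%/70%.

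**The case against.** The strongest reply is that the MTD definition governs. It is stated four times, including in the primary-endpoint section. The MTD label in this branch comes from a specimen clause and a sample-size note, and 7.3, whose enrollment status line is later (October 2021 against April 2021 in 14.1), does not use it. Ten patients will have been treated at dose level 2, so a team could apply 14.3.2 and avoid the effect. That is true, and the probabilities above assume that 14.1 is followed literally. But no text tells the team to do this, and none says what follows if 2 or more of 6 have a DLT.

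The effect is also modest and is not pure error. At assumed rates of 10% or 20% at dose level 2, the 1.2 and 4.1 points largely represent keeping a dose many would accept. The protocol states no target DLT rate to settle this. That stands, and it is counted below as a cost of the fix.

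The narrow reading of the reopening rule can be challenged too. Read that way, the synopsis and 1.2 give no instruction for 2 or more DLTs in the first 3 at any level, which looks like a drafting gap. A broader reading would make the conflict with this branch wider.

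On donors, 14.1 says its aim is 10 at the MTD, so one could enrol more patients instead of correcting the number. Three DLT-cohort patients followed by 7 expansion patients give 10 donors and 6+3+6+10 = 25, exactly the maximum in 14.2. That is a legitimate choice, but it costs 3 patients, whereas restating 7 costs none. Section 13.2 also confines the immunome work to the expansion phase. On that basis the branches give 10, 10, 7, 4, 4 and 7, so an immunome shortfall would not be unique to this branch. It does not rescue the 10 stated here.

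**Conclusion.** Both parts hold, and the point should be fixed. Followed as written, the last branch of 14.1 names dose level 2 the MTD without the 6-patient evidence that the plan's definition requires, and neither 14.1 nor 7.3 supplies the check or its consequence. Over the assumed rate pairs, the chance of naming a level that would fail at 6 is 1.2 to 7.3 percentage points, given that dose level 2 is opened. This rests on assumed DLT rates and on a team that does not apply 14.3.2 of its own accord. It concerns one conditional branch, and the documents do not show whether the trial reached it. The all-patient safety analysis in 14.3 and the twice-yearly DSMB review in 15.12 limit harm to patients, so the main risk is a mislabelled MTD. The donor figure is a plain count and does not depend on the assumed rates: 7, not 10.

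**What to change.** In this branch of both 7.3 and 14.1:

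- Make the first 3 of the 7 added patients the DLT cohort that brings dose level 2 to 6, and name it the MTD only if at most 1 of the 6 has a DLT.
- Restate specimen donors at the MTD as 7. The maximum total stays at 22.
- If 2 or more of the 6 have a DLT, expand at dose level 1 with up to 7 patients. With 3 to 6 patients at dose level 3, the total is 6+6+(3 to 6)+7 = 22 to 25, within the maximum in 14.2. The 10 patients used in the existing dose-level-1 branches would give 25 to 28 and could exceed it.

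This is a change of protocol wording and adds no patients when dose level 2 holds. It has three costs:

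- A one-cycle pause for DLT assessment after the first 3 added patients.
- A lower chance of naming a tolerable dose level 2: 54.3% to 50.2% at assumed rates of 20%/40%, and 52.5% to 51.4% at 10%/30%.
- If dose level 2 fails at 6, up to 3 more patients than the branch now plans (22 to 25 against 19 to 22), with at most 7 in the dose-level-1 expansion.
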